1 SYNOPSIS

Title: A Randomized, Double-Blind, Placebo-Controlled Study to Evaluate the Safety and Efficacy of ABBV-154 in Subjects with Moderately to Severely Active Crohn's Disease (CD): AIM-CD	
Background and Rationale:	
ABBV-154 is an antibody-drug conjugate (ADC) composed of adalimumab (the active component of Humira[®]) conjugated to phosphorylated A-1677770, a proprietary glucocorticoid receptor modulator (GRM, also referred to as the GRM payload), which is being developed for the treatment of immune-mediated inflammatory diseases. ABBV-154 has the potential to deliver an anti-inflammatory payload to activated immune cells that express transmembrane tumor necrosis factor and minimize systemic exposure to the free GRM payload. Therefore, ABBV-154 is a promising novel therapeutic agent which may achieve transformational efficacy while reducing side effects caused by systemic glucocorticoid exposure.

Objective(s) and Endpoint(s):	
Primary Objective: To assess the efficacy, safety, and tolerability of ABBV-154 in comparison with placebo in subjects with moderately to severely active CD who had inadequate response to or were intolerant of prior biologics.
 
Secondary Objectives: To assess the pharmacokinetics (PK), pharmacodynamics (PD), and immunogenicity of ABBV-154.
 
Primary Endpoint: Achievement of endoscopic response at Week 12 in the Induction Period defined as a decrease in Simple Endoscopic Score for Crohn's Disease (SES-CD) > 50% from Baseline (or for subjects with isolated ileal disease and a Baseline SES-CD of 4, at least a 2-point reduction from Baseline).
 
Secondary Endpoints: Achievement of the following:
 
 • Clinical remission per Crohn's Disease Activity Index (CDAI) at Week 12 in the Induction Period defined as a CDAI < 150. • Clinical remission per average daily liquid or very soft stool frequency (SF) and average daily abdominal pain (AP) score (SF/AP) at Week 12 in the Induction Period defined as average daily liquid or very soft SF ≤ 2.8 and not worse than Baseline AND average daily AP score ≤ 1 and not worse than Baseline. • Endoscopic response per SES-CD at Week 40 in the Maintenance Period. • Clinical remission per CDAI at Week 40 in the Maintenance Period. • Clinical remission per SF/AP at Week 40 in the Maintenance Period. 
All endoscopic endpoints will be scored by a central reviewer.

Investigator(s):	Multicenter
Study Site(s):	Approximately 200 sites, globally.

Study Population and Number of Subjects to be Enrolled:	265 adults with moderately to severely active CD who had inadequate response to or were intolerant of prior biologics
Investigational Plan:	
This is a randomized, double-blind, placebo-controlled Phase 2b study to assess the safety, tolerability, PK, PD, immunogenicity, and efficacy of ABBV-154 in subjects with moderately to severely active CD who had inadequate response to or were intolerant of prior biologics. The enrollment for subjects with prior adalimumab use is capped at approximately 30% of the total enrolled subjects. The study comprises 3 periods: a 12-Week Double-Blind Placebo-Controlled Induction Period, a 12-Week Double-Blind Re-Induction Period (for subjects who are considered as clinical non-responders and endoscopic non-responders), and a 40-Week Double-Blind Placebo-Controlled Maintenance Period.
 
At the Baseline Visit of the Induction Period, approximately 265 subjects will be randomized in a 1:1:1:1:1 ratio into 4 ABBV-154 treatment groups or placebo:
 
 1. Induction Group 1: Loading dose of 150 mg intravenously (IV) at Week 0, followed by 80 mg subcutaneous (SC) at Week 2 and every other week (EOW); 2. Induction Group 2: Loading dose of 300 mg IV at Week 0, followed by 230 mg SC at Week 2 and EOW; 3. Induction Group 3: Loading dose of 600 mg IV at Week 0, followed by 530 mg SC at Week 2 and EOW; 4. Induction Group 4: Loading dose of 600 mg IV at Week 0, followed by 530 mg SC at Week 4 and 8 and placebo at Weeks 2, 6, and 10; and 5. Induction Group 5: Matching placebo (IV and SC). 
At Week 12 of the Induction Period, subjects achieving clinical response, defined as a decrease in CDAI \geq 100 points from Baseline (CR100) of the Induction Period AND/OR endoscopic response (per local read) will receive treatment in the 40-Week Maintenance Period as follows:
 
 1. Induction Group 1: Re-randomized in a 1:1 ratio to receive ABBV-154 80 mg SC EOW or matching placebo; 2. Induction Groups 2 to 4: Re-randomized in a 1:1:1 ratio to receive ABBV-154 80 mg SC EOW, ABBV-154 230 mg SC EOW, or matching placebo; 3. Induction Group 5: ABBV-154 80 mg SC EOW 
At Week 12 of the Induction Period, subjects who are categorized as clinical non-responders and endoscopic non-responders (per local read) will be re-randomized into the Re-Induction Period. Subjects who demonstrate inadequate response at or after Week 8 in the Induction Period may receive Rescue Therapy with oral glucocorticoids (per protocol).
 
Subjects who receive Rescue Therapy, fail to complete glucocorticoid tapering by Week 6, or increase doses of or initiate treatment with aminosaliculates or immunomodulators in the Induction Period will be


	
considered non-responders, regardless of clinical response or endoscopic response (per local read) at Week 12 and will be re-randomized in a 1:1 ratio into 2 ABBV-154 treatment groups in the 12-Week Re-Induction Period as follows:
 
 1. Re-Induction Group 1: Loading dose of 300 mg IV at Week 0, followed by 230 mg SC at Week 2 and EOW; 2. Re-Induction Group 2: Loading dose of 600 mg IV at Week 0, followed by 530 mg SC at Week 2 and EOW. 
Subjects who achieve clinical response AND/OR endoscopic response (per local read) at Week 12 of the Re-Induction Period will be re-randomized into the Maintenance Period as described above for subjects achieving clinical response AND/OR endoscopic response (per local read) at Week 12 of the Induction Period. Subjects who do not achieve either clinical response or endoscopic response (per local read) after the Re-Induction Period will be discontinued and will have a follow-up visit scheduled 70 days after last study drug administration.
 
To determine endoscopic response status for re-randomization into the Maintenance Period, the SES-CD score per local read at Week 12 of the Induction/Re-Induction Period and the SES-CD score per central read at Baseline will be used. In the case of missing data where either clinical response or endoscopic response cannot be determined, subjects will be considered non-responders for the re-randomization criteria evaluation.
 
Subjects who have an inadequate response at or after Week 4 in the Maintenance Period will be eligible to receive Rescue Therapy with a single dose of ABBV-154 600 mg IV followed by ABBV-154 230 mg SC EOW. Subjects who have received rescue therapy with ABBV-154 for at least 4 weeks and who continue to demonstrate inadequate response may receive additional Rescue Therapy with oral glucocorticoids, aminosalicylates, or immunomodulators.
 
The primary analysis for the Induction Period and Re-Induction Period will be performed after all subjects have either completed Week 12 of the Induction Period and Re-Induction Period, respectively, or prematurely discontinued study participation. The final analysis will be conducted after all subjects have either completed Week 40 of the Maintenance Period plus the follow-up visit or prematurely discontinued study participation. To ensure the integrity of the trial, the study sites and subjects will remain blinded until the final database lock is completed.
 
The Wearable Device Substudy will enroll up to approximately 75 subjects in countries and sites where the digital health technology device is deployed and available. For subjects participating in the substudy, data for sleep parameters, daily physical activity, and SF data will be collected continuously throughout the 12-Week Induction Period.

--	--

Key Eligibility Criteria:	
Male or female between 18 and 75 years of age inclusive at the time of Screening.
 
Confirmed diagnosis of CD for at least 3 months prior to Baseline of the Induction Period.
 
CDAI score 220 to 450 at Baseline of the Induction Period.
 
Endoscopic evidence of mucosal inflammation as documented by an SES-CD of ≥ 6 for ileocolonic or colonic disease or SES-CD of ≥ 4 for isolated ileal disease as scored by a central reader. All eligible scores must exclude the presence of narrowing component.
 
Demonstrated intolerance or inadequate response to one or more of the following biologic agents: infliximab, adalimumab, certolizumab pegol, vedolizumab, natalizumab, ustekinumab, or risankizumab. Subjects with prior intolerance to adalimumab are not eligible to enroll.

Study Drug and Duration of Treatment:	
Screening up to 35 days (minimum of 8 days).
 
Overall maximum individual treatment duration is planned for up to 448 days (~64 weeks) with the following:
 
 • Double-Blind Induction Period for 12 weeks with placebo or ABBV-154: Induction Group 1) loading dose of 150 mg IV at Week 0, followed by 80 mg SC at Week 2 and EOW; Induction Group 2) loading dose of 300 mg IV at Week 0, followed by 230 mg SC at Week 2 and EOW; Induction Group 3) loading dose of 600 mg IV at Week 0, followed by 530 mg SC at Week 2 and EOW; Induction Group 4) loading dose of 600 mg IV at Week 0, followed by 530 mg SC at Weeks 4 and 8, and placebo at Weeks 2, 6, and 10; and Induction Group 5) matching placebo. • Double-Blind Re-Induction Period for 12 weeks in subjects who are considered as clinical non-responders and endoscopic non-responders at Week 12 of the Induction Period: Re-Induction Group 1) ABBV-154 300 mg IV at Week 0 of the Re-Induction Period, followed by 230 mg SC at Week 2 and EOW or Re-Induction Group 2) ABBV-154 600 mg IV at Week 0 of the Re-Induction Period, followed by 530 mg SC at Week 2 and EOW; • Double-Blind Maintenance Period for 40 weeks with placebo or ABBV-154 80 mg SC EOW or 230 mg SC EOW; 
Follow-up Period of 70 days after last study drug administration.

Date of Protocol Synopsis:	
20 December 2022

2 INTRODUCTION

2.1 Background and Rationale

Why Is This Study Being Conducted?

There are a number of anti-inflammatory biologic therapies available to treat patients with Crohn's disease (CD), including infliximab, adalimumab, certolizumab pegol, vedolizumab, natalizumab, and ustekinumab. In particular, the efficacy and safety of anti-tumor necrosis factor (anti-TNF) monoclonal antibodies, including adalimumab, in CD is well established.^{1,2,3} Adalimumab demonstrated superior efficacy for inducing and maintaining clinical remission compared to placebo in moderate to severe CD patients who failed conventional therapies and infliximab.^{4,5} However, while the available biologic treatments have provided therapeutic options for CD patients, there remain high treatment failure rates associated with existing agents.⁶ Patients with CD treated with anti-TNF agents do not respond at rates of 10% to 40% to initial treatment (primary nonresponse) and additional subjects are observed to lose response over time (secondary loss of response).⁷ Similar patterns of primary nonresponse and secondary loss of response have been observed with other classes of anti-inflammatory biologics used to treat CD.^{8,9} Despite the availability of multiple advanced therapies for the treatment of CD patients, the overall burden of surgery remains high in this population at 3.8 intestinal resections per 100 person-years. Therefore, a large unmet need remains for the treatment of CD.¹⁰

Glucocorticoids have been shown to be efficacious for inducing clinical remission in CD. While nontargeted glucocorticoids with systemic exposure and limited systemic exposure have not been shown to be effective for maintenance treatment,¹¹ approximately 25% of CD patients are glucocorticoid-dependent receiving chronic or recurrent systemic glucocorticoids.^{12,13,14,15} However, the administration of glucocorticoids is limited due to their long-term side effect profile including (but not limited to) hypothalamic-pituitary-adrenal axis (HPA) suppression, osteoporosis, hyperglycemia, glaucoma, and skin atrophy.¹⁶ Thus, the full efficacy of glucocorticoid therapy is often limited with existing agents due to systemic side effects.

ABBV-154 is an anti-TNF antibody-drug conjugate (ADC) composed of adalimumab (the active component of Humira®) conjugated to phosphorylated A-1677770, a proprietary glucocorticoid receptor modulator (GRM, also referred to as the GRM payload) via an [REDACTED] linker. Binding of the adalimumab portion of the ABBV-154 ADC to activated immune cells that express transmembrane TNF is intended to deliver the anti-inflammatory payload intracellularly. The monoclonal antibody portion of the ADC provides targeted delivery of the GRM payload to minimize systemic exposure to the free GRM payload. Therefore, ABBV-154 is a promising novel therapeutic agent which may achieve transformational efficacy while reducing side effects caused by systemic glucocorticoid exposure.

This is a dose-ranging study to explore the efficacy and safety of ABBV-154 in subjects with moderately to severely active CD who continue to have unmet medical need, and to inform subsequent clinical studies in the indication.

2.2 Benefits and Risks to Subjects

The clinical efficacy of TNF inhibitors and glucocorticoids in the treatment of CD is well established. By utilizing expression of transmembrane TNF on activated immune cells, ABBV-154 has the potential to deliver an anti-inflammatory payload intracellularly, while minimizing systemic exposure to the free GRM payload. Based on the data discussed in the ABBV-154 Investigator's Brochure, ABBV-154 is expected to demonstrate a positive benefit-risk profile for the treatment of CD.

Medical review of the safety data from the Phase 1, single ascending dose study did not identify any unexpected risk or trend in the healthy volunteer population (including Japanese and Chinese subjects). For further details, please see the ABBV-154 Investigator's Brochure.

In clinical settings, TNF antagonists and glucocorticoids have been associated with increased risk for serious infections due to bacterial, mycobacterial, invasive fungal, viral, parasitic, or other opportunistic pathogens. Subjects with a recent history of these events will be excluded from the study. Other known adverse events (AE) for glucocorticoids include hypertension, hypothalamic pituitary-adrenal axis (HPA) suppression, decreased bone-formation, diabetes, glaucoma, and cataracts. Signs of infection, blood pressure changes, blood glucose levels, HPA axis suppression, and bone mineral density will be closely monitored during the study.

TNF antagonists have also been associated with an increased risk for serious allergic reactions, including anaphylaxis; infusion reactions; malignancy (including nonmelanoma skin cancer [NMSC], lymphoma, and leukemia); worsening or new onset heart failure; and rarely hepatitis B virus (HBV) reactivation, central nervous system events, demyelinating disease, pancytopenia (including aplastic anemia), and lupus-like syndrome. Subjects with a history of these events, other than successfully treated NMSC or localized carcinoma in situ of the cervix, will be excluded from the study. Signs and symptoms of these events will be closely monitored.

The safety profile specific to the adalimumab component of ABBV-154 is well-established for marketed doses. In addition, adalimumab has been studied at doses up to 10 mg/kg intravenously (IV), which is higher than the doses planned in this study, with a safety profile consistent to Humira® product labeling. Potential risks will be minimized through the selection of appropriate study subjects defined by the eligibility criteria and subject safety will be monitored by an unblinded independent data monitoring committee (DMC) and regular blinded review of safety data by the study team (see Section 5.10). In addition, guidance for toxicity management and stopping rules are provided to ensure subject safety (see Section 6.2).

Based on the totality of the data, ABBV-154 is expected to demonstrate therapeutic benefit in the treatment of CD with a positive benefit-risk profile for development in the treatment of this disease.

In view of the coronavirus pandemic 2019 (COVID-19), the benefit-risk profile of various immunomodulatory therapies on COVID-19 are being evaluated. Currently, the effects of ABBV-154 on the course of COVID-19 are not well defined. Guidance regarding severe acute respiratory syndrome coronavirus 2 (SARS-CoV-2) vaccination is provided for investigators in Section 5.4.

The safety and effectiveness of the device component (non-investigational device) for use as described in labeling has been demonstrated through literature review, pre-clinical, and clinical data as

appropriate, and the device is certified, cleared, approved, or registered for marketing. The benefits of the device in use, as labeled and as planned for this clinical study, have been demonstrated to outweigh the residual risks.

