5 STUDY ACTIVITIES

5.1 Eligibility Criteria

Subjects must meet all of the following criteria in order to be included in the study. Anything other than a positive response to the questions below will result in exclusion from study participation. (In this section, "Baseline" refers to the Baseline [Week 0, Day 1] of the Induction Period.)

Consent

- ✓ 1. Subject must be able to understand and willing to adhere to all protocol requirements and voluntarily sign and date an informed consent, approved by an independent ethics committee (IEC)/institutional review board (IRB), prior to the initiation of any screening or study-specific procedures.

Demographic and Laboratory Assessments

- ✓ 2. Adult **male or female**, at least 18 years old and not more than 75 years of age at the time of Screening.
- ✓ 3. Body Mass Index (BMI) ≥ 18.0 to ≤ 39.9 kg/m² after rounding to the nearest tenth at the time of Screening. BMI is calculated as weight in kg divided by the square of height measured in meters.
- ✓ 4. **Laboratory values** must meet the following criteria within the Screening Period:
 - Serum aspartate aminotransferase (AST) $\leq 2.5 \times$ upper limit of normal (ULN);
 - Serum alanine transaminase (ALT) $\leq 2.5 \times$ ULN;
 - Total bilirubin $\leq 1.5 \times$ ULN;
 - Estimated glomerular filtration rate (eGFR) by simplified 4-variable Modification of Diet in Renal Disease formula ≥ 60 mL/min/1.73 m²;

- Absolute neutrophil count (ANC) \geq 1,500/ μ L;
- Absolute lymphocyte count (ALC) \geq 800/ μ L;
- Platelet count \geq 75,000/ μ L;
- Glycated hemoglobin (hemoglobin A1c [HbA1c] \leq 8.5%);
- Serum potassium $>$ 3.0 mmol/L and $<$ 5.5 mmol/L; and
- Thyroid-stimulating hormone $<$ 10.0 mIU/L.

Disease/Condition Activity

- ✓ 5. Subject must have a confirmed diagnosis of CD for at least 3 months prior to Baseline. Appropriate documentation of biopsy results consistent with the diagnosis of CD, in the assessment of the Investigator, must be available.
- ✓ 6. Subject must have a CDAI score of 220 to 450 at Baseline.
- ✓ 7. Subject must have endoscopic evidence of mucosal inflammation as documented by an SES-CD of \geq 6 for ileocolonic or colonic disease or SES-CD of \geq 4 for isolated ileal disease as scored by a central reader. All eligible scores must exclude the presence of narrowing component.

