 - Uncontrolled hypertension defined as confirmed systolic blood pressure > 160 mm Hg or diastolic blood pressure > 100 mm Hg at rest despite regular treatment under standard of care.
 - Glaucoma, osteonecrosis, or osteoporosis with high risk of fracture (e.g., T score ≤ -2.5 with history of fragility fracture).
 - Organ transplant which requires continued immunosuppression.
 - Demyelinating disease (including myelitis) or neurologic symptoms suggestive of demyelinating disease.
 - Active or suspected malignancy or history of any malignancy within the last 5 years, except for successfully treated nonmelanoma skin cancer (NMSC) or localized carcinoma in situ of the cervix. Regardless of the time since remission, subjects with any history of lymphoma, leukemia, melanoma, Merkel cell carcinoma, colon carcinoma, or small bowel carcinoma.
 - History of any medical condition other than CD that is likely to require systemic glucocorticoid treatment during the study (e.g., asthma and chronic obstructive pulmonary disease [COPD]) per investigator judgement.
 - Allergic reaction or significant sensitivity to constituents of the study drug (and its excipients) and/or other products in the same class. This includes anaphylactic reaction to any agent (e.g., food products or bee sting), hereditary fructose intolerance, or a reaction to any immunoglobulin G (IgG) containing product.
 - Dysplasia of the gastrointestinal tract or found to have dysplasia, other than completely removed low-grade dysplastic lesions, in any biopsy performed during the Screening endoscopy.
 - Hepatic cirrhosis.
- ✓ 15. For subjects in the Wearable Device Substudy, subjects with history of pre-existing sleep disorders, including insomnia requiring regular sleep medication, obstructive sleep apnea, restless leg syndrome, or currently on prescription sleep medications should not participate in the Wearable Device Substudy but may participate in the study as a whole if meeting all other eligibility criteria.
- ✓ 16. Subject must not have a history of clinically significant (per investigator's judgment) drug or alcohol abuse within the last 12 months prior to Baseline.

- ✓ 17. There must be no reason the investigator believes that the subject is an unsuitable candidate to participate in the study, receive study drug, or would be placed at risk by participating in the study (e.g., because of a medical condition or illness other than CD that is not well controlled regardless of treatment).

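### Protocol Section 2.2 says a history of pancytopenia/aplastic anaemia or lupus-like syndrome excludes a subject, but no criterion in Section 5.1 names either history

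*Protocol*

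**What the plan says.** Section 2.2 of the protocol sets out risks known for TNF antagonists. The list ends with "pancytopenia (including aplastic anemia), and lupus-like syndrome". The next sentence reads: "Subjects with a history of these events, other than successfully treated NMSC or localized carcinoma in situ of the cervix, will be excluded". It gives two exceptions, both for malignancy, and no limit of time or severity. The preceding paragraph, on infections, restricts its exclusion to a recent history; this sentence does not.

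Section 2.2 then says how that selection is to be achieved: "Potential risks will be minimized through the selection of appropriate study subjects defined by the eligibility criteria". Section 5.1 is the operative list: "Subjects must meet all of the following criteria in order to be included in the study".

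Section 5.1 bears on the two histories in five places:

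- Criterion 4 sets laboratory limits that subjects "must meet the following criteria within the Screening Period".
- Criterion 12 requires intolerance or inadequate response to at least one listed biologic, and bars anyone with prior intolerance to adalimumab.
- Criterion 14, allergy entry, covers "Allergic reaction or significant sensitivity to constituents of the study drug (and its excipients) and/or other products in the same class" and extends to "a reaction to any immunoglobulin G (IgG) containing product".
- Criterion 14, glucocorticoid entry, covers "History of any medical condition other than CD that is likely to require systemic glucocorticoid treatment during the study".
- Criterion 17 excludes anyone the investigator considers unsuitable.

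**The concern.** The benefit-risk statement tells ethics committees, regulators and sites that these two histories are kept out of the trial. Sites enrol from Section 5.1, where neither is named. The study drug is an adalimumab conjugate, so these are histories that the protocol itself ties to the drug's antibody component. If the list is followed exactly, one site may enrol such a subject and another may refuse, depending on how a general clause is read. The stake is subject safety at entry and the accuracy of the benefit-risk statement, not the efficacy analysis.

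**Working it through.** No arithmetic beyond counting applies. The check compares the Section 2.2 sentence with criteria 1 to 39 of Section 5.1.

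**Step 1: is either history named?** Criterion 14 holds the disease-history list. Its entries are adrenal insufficiency; untreated hypothyroidism; heart failure; uncontrolled hypertension; glaucoma, osteonecrosis or high-risk osteoporosis; organ transplant; demyelinating disease; malignancy; conditions likely to need systemic glucocorticoids; allergy or sensitivity; gastrointestinal dysplasia; and cirrhosis. That is 12 entries, and 0 of the 12 name pancytopenia, aplastic anaemia or lupus-like syndrome. No other criterion names them.

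**Step 2: what catches them indirectly?**

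| Section 5.1 clause | What it catches | What it leaves open |
|---|---|---|
| Criterion 12, adalimumab intolerance | Firmly excludes either event if recorded as adalimumab intolerance | Events on another agent or from another cause |
| Criterion 4, laboratory limits | Low counts at screening: ANC below 1,500, ALC below 800, platelets below 75,000 per microlitre | A resolved event; 3 of the 10 limits are blood counts and none is a haemoglobin concentration |
| Criterion 14, allergy entry | Possibly an event caused by a same-class or IgG product, if the wording is read broadly | Events from other causes; on a narrow reading, anything not allergic in nature |
| Criterion 14, glucocorticoid entry | A condition expected to need systemic glucocorticoids during the study | A past event with no expected need |
| Criterion 17 | Whatever the investigator judges unsuitable | No fixed rule |

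**Step 3: two test cases.**

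1. A subject stopped infliximab because of a lupus-like syndrome, since resolved, and never took adalimumab. Under criterion 12 the infliximab intolerance counts towards entry. Criterion 4 is not engaged if counts are normal. Exclusion then turns on whether the allergy entry is read to include this kind of reaction, or on criterion 17. Section 2.2 says the subject is excluded.
2. A subject had pancytopenia from a cause unrelated to any biologic and has recovered to counts above the three limits. Criteria 4 and 12 do not exclude the subject, the allergy entry does not reach the cause, and no glucocorticoid need is expected. Only criterion 17 remains. On its plain wording, Section 2.2 again says the subject is excluded.

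**Step 4: the other events in the same sentence.** Section 5.1 sets explicit limits for heart failure (NYHA Class III or IV), malignancy (within 5 years, or six named types at any time), HBV (current surface antigen or detectable DNA) and neurological events (demyelinating disease or suggestive symptoms). Here Section 2.2 is a looser summary of stated rules. For HBV, Table 3 in Section 6.2 plans for enrolled subjects who are core-antibody positive and DNA negative, which shows that the criterion is as intended.

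**The case against.** The strongest reply is that Section 2.2 is narrative and itself defers to the eligibility criteria, so a loosely worded summary creates no conflict at enrolment. That stands for heart failure, malignancy, HBV and neurological events, where an explicit criterion exists. It does not dispose of the two histories for which no criterion exists to defer to.

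A second reply is that Section 5.1 is not silent. Criterion 12 is a hard exclusion for the antibody contained in the study drug, and it needs no judgement once intolerance is recorded. Pancytopenia is also partly screened by the count limits. Both points stand and narrow the gap. They do not close it for a resolved event, or for one on another anti-TNF agent or from another cause.

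A third reply is that the phrase in Section 2.2 refers back to events associated with TNF antagonists, so only drug-associated histories may be meant. That reading is possible. It would remove the second test case but not the first.

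General safeguards also apply after entry. Section 5.5 stops study drug when an adverse event rules out safe continuation, Section 6.1 collects adverse events to 70 days after study drug is stopped, and Table 3 interrupts dosing for low neutrophils, lymphocytes or platelets. These limit the consequence, but they act after exposure.

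**Conclusion.** The inconsistency is real and minor. Two histories that Section 2.2 says are excluded have no criterion of their own in Section 5.1, and the indirect cover is incomplete. There is no effect on endpoints, power or analysis. The number of subjects affected cannot be derived from the documents. Section 2.2 calls these events rare with TNF antagonists, but that does not give the frequency of such a history from any cause in this population.

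Three stronger readings are tempting and are not supported:

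- A reader might infer that nothing in Section 5.1 protects these subjects. Criterion 12 and the count limits show otherwise.
- A reader might infer that the criteria must be the part in error. The documents do not show which section reflects the sponsor's intent.
- A reader might infer that the narrower limits for heart failure, malignancy, HBV or neurological events are further safety gaps. They are explicit rules, and nothing in the documents shows them to be unsafe.

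The conclusion assumes that Section 5.1 is the complete eligibility list, as it presents itself. The Operations Manual was not available for this check.

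**What to change.** Add a history of lupus-like syndrome and a history of pancytopenia or aplastic anaemia to criterion 14. The sponsor should say whether any cause counts or only drug-associated events. The cost is protocol wording at the next amendment and possibly a few screen failures.

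If the sponsor does not intend these exclusions, correct the Section 2.2 sentence instead so that it claims only what Section 5.1 delivers. That costs wording alone, but makes the benefit-risk statement slightly less favourable.

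In either case, the same sentence can be aligned editorially with the Section 5.1 limits for heart failure, malignancy, HBV and neurological events. That changes nothing in the conduct of the trial.
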